8.7. Landmark Survival

KM estimates of OS at 180, 360, 540 and 720 days will be summarized. Comparisons between the two treatment groups will be made using independent Z tests.

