2.2. Secondary Objectives

The secondary objectives of this study are:

- Phase-1b and -2 portions: To determine the PK of tarextumab in combination with EP in subjects receiving first-line therapy for ES-SCLC
- Phase-1b and -2 portions: To determine the immunogenicity of tarextumab in combination with EP in subjects receiving first-line therapy for ES-SCLC
- Phase-2 portion: To estimate the improvement in overall survival (OS), 12-month survival and overall response rate (ORR) resulting from the addition of tarextumab to EP in subjects receiving first-line therapy for ES-SCLC

- Phase-2 portion: To correlate the treatment effect in PFS, OS, 12-month survival and ORR resulting from the addition of tarextumab to EP in subjects with Notch3, Hey2, Hes1, Hey1 and Hes6 expression
- Phase-1b portion: To determine the safety and tolerability of tarextumab in combination with EP in subjects who are receiving first-line therapy for ES-SCLC
- Phase-2 portion: To compare the safety and tolerability of tarextumab in combination with EP relative to EP alone in all subjects who are receiving first-line therapy for ES-SCLC

Statistical analyses concerning the secondary objectives for the phase-1b portion of this study will not be addressed in this SAP.

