Subjects may continue one of the chemotherapy drugs if the other is held or discontinued prior to completing 6 cycles of EP and prior to disease progression. Subjects should continue EP alone for a total of 6 cycles if tarextumab is held or discontinued prior to the completion of 6 cycles of EP. Subjects may continue study drug if one or both of the chemotherapy drugs is held or discontinued prior to completing 6 cycles of EP and prior to disease progression.

The phase-2 portion of the study may commence after the safety and tolerability of the highest tolerable dose of tarextumab has been confirmed in both cohorts of subjects with etoposide and cisplatin/carboplatin during phase-1b. The highest tarextumab dose that is tolerable with both platinum options will be used in the phase-2 portion of the study. For example: if tarextumab at 15 mg/kg is tolerable with etoposide and cisplatin, but not tolerable with etoposide and carboplatin; and tarextumab at 12.5 mg/kg is tolerable with etoposide and carboplatin, then tarextumab at 12.5 mg/kg will be the dose used in phase-2. The phase-2 portion includes a blinded treatment phase and follow-up phase. It is a multicenter, randomized, placebo-controlled portion evaluating the efficacy and safety of tarextumab in combination with etoposide and platinum therapy in subjects with previously untreated ES-SCLC. Subjects may be treated with cisplatin or carboplatin as determined by the Investigator prior to randomization. Alteration to the choice of platinum therapy is not permitted once the subject is randomized.

Approximately 135 evaluable subjects will be enrolled to the phase-2 portion of the study. Evaluable subjects are those who received at least one dose of study drug (either tarextumab or placebo).

Version 1.1 of standard response evaluation criteria in solid tumors (RECIST) criteria [Ref-1] was used to evaluate patients' responses to treatment. RECIST response categories include complete response (CR), partial response (PR), stable disease (SD) and progressive disease (PD). In addition to these four primary ratings, a patient's response to treatment is classified as unevaluable (abbreviated NE) when no imaging/measurement is performed at a particular time point.

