3.1. Blinded Treatment Phase

Subjects who qualify for enrollment into the phase-2 portion of the study will be randomized in a 1:1 ratio to receive study treatment of EP with placebo or EP with tarextumab. The randomization will be balanced on the choice of platinum therapy (cisplatin versus carboplatin) and the prior use of whole brain radiation (WBR) or prophylactic cranial irradiation (PCI). Changing the choice of platinum therapy is not permitted once the subject is randomized. Treatment for each subject will begin on Cycle 1, Day 1 (the first dosing day). Etoposide 100 mg/m² will be given on Days 1, 2 and 3 and cisplatin 75 mg/m² or carboplatin to an AUC of 5 mg/mL/min will be given on Day 1 of every 21-day cycle for 6 cycles. Subjects may remain in the blinded treatment phase to continue one of the chemotherapy drugs if the other is held or discontinued prior to completing 6 cycles of EP and prior to disease progression. For subjects who have study drug held or discontinued for tolerability reasons, EP chemotherapy should continue to the completion of 6 cycles. Subjects may continue study drug if one or both of the chemotherapy drugs is held or discontinued prior to completing 6 cycles of EP and prior to disease progression.

After the completion of 6 cycles of EP, subjects who do not have disease progression and have not had WBR or PCI prior to study entry and are good candidates for PCI according to the

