Analyses 1 and 2 will take place at the last two quarterly safety review meeting of the Data Safety Monitoring Board (DSMB). The estimated numbers of events at these times are presented in Table 1. If the number of events differs from what is presented, then the efficacy and safety boundaries will be recalculated using the spending functions which are footnoted in Table 1.

Overall survival is a secondary endpoint in this study. An analysis of OS will take place at the time of each analysis for PFS as well as at the time that the final analysis of PFS takes place. The final analysis of OS will take place when there are 98 events or 6 months after the final analysis for PFS, whichever occurs first. Table 2 and Figure 1 present enrollment, PFS events and Deaths over time assuming a control hazard of progression beyond 9 months of 0.1386.

[figure not shown]
Table 2. Enrollment, Progressions and Deaths over Time – Control Hazard of Progression of 0.1386 Beyond 9 Months

Study Time (months)	6	12	13	14	15	16	17	18	19	20
Cumulative Enrolment	22	77	85	89	91	105	119	133	134	134
Total PFS Events	5	31	38	43	49	55	62	69	75	80
Total PFS Events-2 [1]	6	35	42	48	54	61	68	76	82	87
Total Deaths	3	19	23	27	32	37	42	49	55	61
Total Deaths-2 [1]	4	22	27	32	37	42	49	56	63	69
Censored PFS (tarextumab)	1	5	6	7	8	9	10	11	12	13
Censored PFS (placebo)	1	4	5	6	7	8	9	9	10	11

Study Time (months)	21	22	23	24	25	26	27	28	29	30
Cumulative Enrolment	134	134	134	134	134	134	134	134	134	134
Total PFS Events	85	90	94	96	97	98	99	99	100	100
Total PFS Events-2 [1]	92	98	101	103	104	104	105	105	105	106
Total Deaths	66	72	77	81	86	91	95	99	102	105
Total Deaths-2 [1]	75	81	86	91	96	100	104	108	111	114
Censored PFS (tarextumab)	14	15	15	16	16	16	16	16	16	17
Censored PFS (placebo)	12	12	13	13	13	13	13	13	13	13

[1] Total PFS Events-2 and Total Deaths-2 refer, respectively, to the expected numbers of progressions and deaths when tarextumab does not prolong progression or death.

Figure 1. Enrollment, Progressions and Deaths over Time – Control Hazard of Progression of 0.1386 Beyond 9 months

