Calculations in Table 2 and Figure 1 take into account non constant hazards for PFS and OS described in Table 3 and Table 4, respectively. Estimates of non constant hazard are from Kaplan-Meier (KM) curves for PFS and Survival in Noda et al [Ref-2] and Hanna et al [Ref-3]. Regarding enrollment it was initially assumed that there is a ramp up time of 5 months with a starting enrollment of 4 subjects per months and that the maximum enrollment rate is 6 subjects per month. The enrollment in Table 10 and Figure 1 represents the observed enrollment up to January 2016 and the remaining enrollment is assumed to be 15 subjects per month.

The censoring rate was initially assumed to be 40% of the rate at which events occur in the control arm and 60% of the rate at which events occur in the tarextumab arm. When 79 PFS events accrued in the study, there were 39 censored observations for a censoring rate of $39/(39+79)=33\%$. This information was used to recalibrate the total number of events at the final analysis, the type 1 error rate and power.

Table 3. Hazards for Piece-Wise Exponential Model of Progression Free Survival

Period	0-5 months	5-7 months	7-8 months	>8 months
% Change in Proportion without an event (Change in PFS)	0.50 (1.00 to 0.50)	0.50 (0.50 to 0.25)	0.50 (0.25 to 0.125)	0.50 (0.125 to 0.0625) 8-18 months [1] 8-11 months [2]
Hazard Control	0.1386	0.3466	0.6931	0.0693, 0.2310
Hazard Treatment	0.0901	0.2253	0.4505	0.0451, 0.1502
Hazard Ratio	0.65	0.65	0.65	0.65

[1] Noda et al [Ref-2]

[2] Hanna et al [Ref-3]

Table 4. Hazards for Piece-Wise Exponential Model of Overall Survival

Period	0-5 months	5-7 months	7-8 months	>8 months
% Change in Proportion without an event	0.50 (1.00 to 0.50)	0.50 (0.50 to 0.25)	0.60 (0.25 to 0.10)	0.467 (0.15 to 0.08) 18-24 months [1]
Hazard Control	0.07702	0.1155	0.1703	0.127
Hazard Treatment	0.05006	0.07509	0.1107	0.0825
Hazard Ratio	0.65	0.65	0.65	0.65

[1] Hanna et al [Ref-3]

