5. GENERAL ANALYSIS CONSIDERATIONS

The statistical analyses will be reported using summary tables, figures and listings (TFLs). Unless otherwise noted, all statistical testing will be two-sided and will be performed at the 0.05 level of significance.

- Continuous variables will be summarized with the number of non-missing values, estimated means, standard deviations, medians, 25th and 75th percentiles, and observed minimum and maximum values.
- Categorical variables will be summarized by counts and by percentages. The percentage of patients within a category will be displayed in parentheses rounded to the nearest tenth of one percent. However, when the number of patients within a category is 0, then the percentage (i.e., 0.0%) will be omitted.
- Time-to-event variables will be summarized by KM estimates of quartiles, observed minimum and maximum values, and the number of censored observations. The hazard will be estimated by the sum of all individual follow-up times in days divided by 365.25.

Any durations of time expressed in months will be reported in proportional “months” according to the formula

$$\text{months} = \frac{365.25}{12} \text{ days.}$$

Summary tables will be presented by treatment group. Individual subject data will be presented in data listings.

The analyses described in this plan are considered *a priori*, in that they have been defined prior to database lock and prior to breaking the treatment blind. If any *a posteriori* analyses (i.e., analyses not included in this SAP) are performed, they will be identified as such in the CSR where the objective and rationale for executing any *a posteriori* analyses will be documented.

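### The 720-day landmark Z test has about 0–2 patients per arm at risk and no rule for a survival curve that is at zero or has ended, so its nominal 5% level is unreliable

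*SAP*

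**What the plan says.** SAP Section 8.7 states that "KM estimates of OS at 180, 360, 540 and 720 days will be summarized" and that "Comparisons between the two treatment groups will be made using independent Z tests". Shell Table 14.2.3.1 gives estimate, number at risk, standard error and p-value at each of the four times, and is repeated for the per-protocol population. Section 5 sets the default level: "all statistical testing will be two-sided and will be performed at the 0.05 level of significance".

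Follow-up is limited by Section 4, "The final analysis of OS will take place when there are 98 events" (or 6 months after the final PFS analysis, if sooner), and by Section 8.6 rule 3, which censors every surviving patient on the day after the 98th death. Section 6 allows the OS cut to be delayed, but under rule 3 a delay adds no follow-up once 98 deaths have occurred.

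The SAP gives no transformation for the Z test, no minimum number at risk, no rule for an estimate of zero and no rule for a curve that stops before the landmark. The related objective in Section 2.2 names only "12-month survival and overall response rate (ORR").

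**The concern.** 720 days is almost 24 months, and the SAP expects its last death-driven cut at about month 25 to 28. Only the first few months' enrollees can have been followed that long, and on the planning hazards few of them survive.

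The Z test divides the difference in survival by the root of the summed Greenwood variances. An arm whose last patient under observation has died has an estimate of zero and an estimated variance of zero, so the test treats that arm as known exactly. A nominally significant two-year difference can then depend on which arm happens to hold the last survivor. How such cases are handled is left to programming.

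**Working it through.** **Inputs**
- Allocation: each patient "will be randomized in a 1:1 ratio to receive study treatment of EP with placebo or EP with tarextumab".
- Size and accrual: "Approximately 135 evaluable subjects will be enrolled to the phase-2 portion of the study"; Table 2 shows 22 by month 6, 77 by month 12, 133 by month 18 and 134 by month 19. Accrual within months 0–6 is not given and is assumed linear.
- Monthly OS hazards (Table 4): "Hazard Control 0.07702 0.1155 0.1703 0.127". The values imply changes at 9, 15 and 18 months; the printed column heads say 5, 7 and 8. The implied times are used, and the printed ones are a sensitivity case.
- OS dropout: no rate is given. Zero is assumed, with 2% per month as a sensitivity case.

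**Reproducing the plan's own figures.** Integrating these hazards over the accrual gives, under the null, 97.2 deaths at month 26 (Table 2: 100) and 111.7 at month 30 (114). At HR 0.65 it gives 96.0 at month 28 (99). A few middle months are up to about 5% low. Table 5 power: √98/2 × |ln 0.682| − 1.036 = 0.858, and Φ(0.858) = 0.8045 (stated 0.8047).

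**Timing.** 720 / (365.25/12) = 23.66 months. Table 2 reaches 98 deaths between months 25 and 26 under the null (96, then 100) and at about month 28 at HR 0.65 (99).

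**Expected number at risk, by hand**
- Control cumulative hazard at 23.66 months: 9 × 0.07702 + 6 × 0.1155 + 3 × 0.1703 + 5.66 × 0.127 = 2.616, so S = exp(−2.616) = 0.073. The printed cut points give 0.062.
- Cut at month 28: enrolled by month 28 − 23.66 = 4.34, which is 22 × 4.34/6 = 15.9 patients. At risk per arm: 15.9 × 0.073 / 2 = 0.58.
- HR 0.65, same cut: the tarextumab arm has S = exp(−0.65 × 2.616) = 0.183, so 15.9 × 0.183 / 2 = 1.45. Simulated at the 98th death: 0.7 control and 1.8 tarextumab.

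**Why a zero curve matters.** Z = |S₁ − S₂| / √(SE₁² + SE₂²). If S₁ = 0 then SE₁ = 0 and Z = S₂/SE₂, so the test rejects whenever SE₂/S₂ < 1/1.96 = 0.51.

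**Null simulation** (8,000–20,000 trials per row, control hazards in both arms, Greenwood SE, |Z| > 1.96)

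| OS cut | Mean at risk per arm | An arm has nobody at risk | A curve is at 0 | Rejects, last value carried forward | Rejects, both curves defined (share of trials) | Rejects, ≥1 at risk in both arms (share of trials) |
|---|---|---|---|---|---|---|
| Month 26 | 0.32 | 92% | 44% | 18.5% | 25.6% (28%) | 4.5% (8%) |
| 98 deaths, or month 28 if earlier | 0.35 | 90% | 44% | 17.0% | 23.6% (30%) | 4.1% (10%) |
| Month 28 | 0.58 | 79% | 35% | 15.3% | 22.3% (43%) | 3.9% (21%) |
| Month 29 | 0.72 | 73% | 31% | 13.8% | 19.6% (48%) | 2.4% (27%) |
| Month 30 | 0.93 | 62% | 25% | 11.9% | 16.4% (56%) | 3.2% (38%) |

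A curve counts as defined if someone is at risk at 720 days or it has already reached zero.

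**Source of the excess.** Where a curve is at zero, about 35–44% of trials reject. Taking the low end at month 28, 35.4% × 0.35 = 12.4% of all trials, out of 15.3%. The other 2.9% come from the 64.6% of trials with no zero curve, a rate of at most 2.9/64.6 = 4.5%. A curve that merely ends early is a different problem: it gives no observed estimate at 720 days.

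**Sensitivity, carried forward:** 14.1% with 2% monthly dropout; 19.0% with Table 4's printed cut points; 8.9% with both arms at the tarextumab hazard (98th death at about month 31, 3.5 at risk per arm); 7.5% at a month-35 cut.

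**Other landmarks** (98 deaths, or month 28 if earlier), carried forward: 5.3% at 180 days, 5.7% at 360 days (16.5 at risk per arm), 7.8% at 540 days (3.6 at risk per arm).

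**The case against.** The strongest reply is that no single error rate can be attributed to this plan. Carrying the last value forward is not in Section 8.7 and sits badly with Section 5.3, which rules out imputation and limits summaries to observed data. If only trials with both curves defined are tested, the rejections amount to about 7–10% of all null trials (for example 23.6% × 29.7% = 7.0%, and 22.3% × 42.7% = 9.5%). That stands: a reader might take 12–18% as the true false-positive rate of the plan, but it belongs to one convention.

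A reader might also infer that having so few patients at risk inflates the test by itself. It does not: with at least one patient at risk in each arm, the test rejects in about 2–5% of null trials.

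The consequences are also limited. No stopping boundary or alpha allocation uses this p-value, and the shell shows the number at risk and standard error beside it, so an empty arm would be visible.

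This does not remove the problem. Seeing a zero at risk does not correct the printed p-value. The test is inflated even in trials where both curves are defined, with no carrying forward. The convention that keeps it near nominal is not stated, and at the 98-death cut it would leave only about 10% of null trials with a 720-day test.

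**Conclusion.** The point holds for the 720-day comparison. As planned it yields either a p-value whose 5% level cannot be relied on or, under the convention that is not inflated, usually no p-value at all. The figures assume Table 2 accrual (linear before month 6), Table 4 hazards with changes at 9, 15 and 18 months, control hazards in both arms, no dropout and cuts from the 98th death to about month 30. Later cuts or better survival reduce the excess.

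It should not be read as a fault of landmark testing in general. The 180- and 360-day tests are close to nominal, so the 12-month objective is sound. The 540-day test is only mildly above nominal. This is a secondary analysis, but one worth correcting because a spurious two-year survival difference could be reported from it.

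**What to change.** In Section 8.7 and Table 14.2.3.1, report 720-day survival descriptively (estimate, number at risk, and confidence interval where defined) with no p-value. Add one general rule: no landmark Z test is done when either arm's estimate is zero or has no patient at risk at that time. A higher minimum may be pre-specified, but this calculation does not single one out. With at least one patient at risk in both arms, the 540-day test rejects in 5.8% of null trials and can still be done in 93% of them.

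The cost is a few lines of SAP and shell text and the loss of one secondary p-value, in the ITT and per-protocol tables, that cannot be interpreted. A log-log scale for the 12-month test is optional. It does not solve the 720-day problem, because it is undefined when the estimate is zero.

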9. EXPLORATORY ANALYSES

An exploratory analysis was undertaken by the sponsor using blinded data to examine the relationship between PFS and the Notch pathway markers HES1, HES6 and NOTCH3. The biomarker values were normalized so that the distributions had mean 0 and variance 1, then a Cox PH model was fit using the three main effects, the three two-way interactions, and the three-way interaction as independent variables. Estimated coefficients are show in Table 6.

Table 6. Cox PH Model between Progression-Free Survival and Three Biomarkers

Independent Variable	Estimated Coefficient	Exponentiated Coefficient	Standard Error	Z-Score	P-Value
HES6	0.17396	1.190	0.192	0.9059	0.3700
HES1	0.00154	1.002	0.134	0.0115	0.9900
NOTCH3	0.01248	1.013	0.189	0.0660	0.9500
HES6*HES1	0.68087	1.976	0.241	2.8300	0.0047
HES6*NOTCH3	-0.56935	0.566	0.247	-2.3021	0.0210
HES1*NOTCH3	0.15654	1.169	0.191	0.8215	0.4100
HES6* HES1*NOTCH3	1.07604	2.933	0.357	3.0175	0.0025

Model notes: n=89 (56 observations deleted due to missing values); number of events=58; Likelihood ratio test=16.3 (7 degrees of freedom); p=0.0222

Judging statistical significance at the two-sided 0.05 level, the two statistically significant terms which included NOTCH3 were used to establish a NOTCH-3-related PFS index (N3RPI).

$$\text{N3RPI} = -0.569 \cdot \text{HES6} \cdot \text{NOTCH3} + 1.076 \cdot \text{HES1} \cdot \text{HES6} \cdot \text{NOTCH3}$$

Patients were then split into two groups (High N3RPI or Low N3RPI) based on whether their score was above or below the median N3RPI (0.066), respectively. A patient whose N3RPI was equal to the median was placed into the Low N3RPI group. Patients in each of these two groups were then split into two additional groups (High NOTCH3 or Low NOTCH3) based on whether their score was above or below the overall median NOTCH3 value (-0.046), respectively. A patient whose NOTCH3 was equal to the median was placed into the Low NOTCH3 group.

The KM curves for PFS and for OS in these four subgroups are presented in Figure 2 and Figure 3, respectively. For patients with an N3RPI above the median N3RPI (i.e., High N3RPI), the difference in PFS between the High and Low NOTCH3 groups is associated with a p-value of 0.09.

Figure 2. Progression-Free Survival Kaplan-Meier Curves for Patients with High and Low N3RPI

[figure not shown]
[figure not shown]

Figure 3. Overall Survival Kaplan-Meier Curves for Patients with High and Low N3RPI

It is noteworthy that high NOTCH3 is trending to be beneficial for patients with low N3RPI, whereas high NOTCH3 appears to be detrimental when N3RPI is high. This prompted the exploratory hypothesis that NOTCH 3 inhibition with tarextumab will improve PFS and OS in patients who have high N3RPI. In the case where N3RPI is high, tarextumab may be able to reduce the detrimental effects associated with high Notch 3 expression.

The following exploratory analyses will be carried out to test this hypothesis. The analysis population (ITT or per-protocol) will be divided into two N3RPI groups: High N3RPI and Low N3RPI (as defined above). Independent Cox PH models will be fit to data from each of the two groups. The models will include effects for treatment (tarextumab or placebo), NOTCH3 value, and the interaction between treatment and NOTCH3. The treatment HR and a 95% CI for the HR will be estimated at the quartiles of the NOTCH3 distribution. The same analysis will be carried out for “high” and “low” patient subgroups based on each of the biomarkers (Hes1, Hes6, Hey1 and Hey2).

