5.4. Subgroup Analyses

Plans for analyses of subgroups based on the presence or absence of anti-tarextumab antibodies are presented in section 11.7 below.

No analyses by baseline characteristics or study center are planned.

Subgroup analyses by baseline Notch3, Hes1, Hey2, Hey1 and Hes6 expression levels are not planned, but the impact these potentially important covariates have on the efficacy of tarextumab will be assessed through statistical modeling (see sections 8.1, 8.3, 8.6 and 8.7).

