Biomarker	Biomarker Level	n	Model Coefficients (SE) ^[1]		Hazard Ratio [95% Confidence Interval] ^[1]		
			Treatment	Treatment x Notch3	At Notch3 25 th Percentile	At Notch3 50 th Percentile	At Notch3 75 th Percentile
N3RPI [2]	High	xx	xx.x (xx.x)	xx.x (xx.x)	xx.xx [x.xx,xx.xx]	xx.xx [x.xx,xx.xx]	xx.xx [x.xx,xx.xx]
	Low	xx	xx.x (xx.x)	xx.x (xx.x)	xx.xx [x.xx,xx.xx]	xx.xx [x.xx,xx.xx]	xx.xx [x.xx,xx.xx]
Hes1	High	xx	xx.x (xx.x)	xx.x (xx.x)	xx.xx [x.xx,xx.xx]	xx.xx [x.xx,xx.xx]	xx.xx [x.xx,xx.xx]
	Low	xx	xx.x (xx.x)	xx.x (xx.x)	xx.xx [x.xx,xx.xx]	xx.xx [x.xx,xx.xx]	xx.xx [x.xx,xx.xx]
Hey2	High	xx	xx.x (xx.x)	xx.x (xx.x)	xx.xx [x.xx,xx.xx]	xx.xx [x.xx,xx.xx]	xx.xx [x.xx,xx.xx]
	Low	xx	xx.x (xx.x)	xx.x (xx.x)	xx.xx [x.xx,xx.xx]	xx.xx [x.xx,xx.xx]	xx.xx [x.xx,xx.xx]
Hey1	High	xx	xx.x (xx.x)	xx.x (xx.x)	xx.xx [x.xx,xx.xx]	xx.xx [x.xx,xx.xx]	xx.xx [x.xx,xx.xx]
	Low	xx	xx.x (xx.x)	xx.x (xx.x)	xx.xx [x.xx,xx.xx]	xx.xx [x.xx,xx.xx]	xx.xx [x.xx,xx.xx]
Hes6	High	xx	xx.x (xx.x)	xx.x (xx.x)	xx.xx [x.xx,xx.xx]	xx.xx [x.xx,xx.xx]	xx.xx [x.xx,xx.xx]
	Low	xx	xx.x (xx.x)	xx.x (xx.x)	xx.xx [x.xx,xx.xx]	xx.xx [x.xx,xx.xx]	xx.xx [x.xx,xx.xx]

^[1] Coefficients, hazard ratios and 95% confidence intervals are from Cox proportional hazards models with effects for treatment, Notch3 and treatment-by-Notch3 interaction. A separate model was used for each biomarker.

^[2] N3RPI is the Notch3-related PFS Index; N3RPI = $-0.569 \times \text{HES6} \times \text{NOTCH3} + 1.076 \times \text{HES1} \times \text{HES6} \times \text{NOTCH3}$

Programmer notes: (a) repeat this table using the per-protocol population

Table 14.2.2.9
Progression-Free Survival – Sensitivity Analysis
Per-Protocol Population

	Placebo (N=xx)	Tarextumab (N=xx)
Total Follow-Up Time (person-years) ^[1]	xxx.x xx (xx.x%) xx (xx.x%)	xxx.x xx (xx.x%) xx (xx.x%)
Number of Subjects with Disease Progression or Death (Censored)		
Hazard ^[2]	0.xx	0.xx
Kaplan-Meier Estimates: Quartiles [95% C.I.] (days)		
25 th Percentile	xxx [xxx,xxx]	xxx [xxx,xxx]
50 th Percentile	xxx [xxx,xxx]	xxx [xxx,xxx]
75 th Percentile	xxx [xxx,xxx]	xxx [xxx,xxx]
Range (Subjects who Progressed or Died) (days)	xxx, xxx	xxx, xxx
Range (All Subjects) (days)	xxx, xxx	xxx, xxx
Hazard Ratio [95% C.I.] ^[3]		x.xx [x.xx,x.xx]
P-value ^[4]		0.xxx

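### Section 9 fits separate treatment models in High and Low N3RPI patients, but no planned analysis estimates whether the treatment effect differs between the two groups

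*SAP*

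**What the plan says.** Section 9 of the SAP builds N3RPI from a Cox model fitted to blinded data and splits patients at its median. It observes that high NOTCH3 tends to go with better outcome when the index is low and worse outcome when it is high. It continues: "This prompted the exploratory hypothesis that NOTCH 3 inhibition with tarextumab will improve PFS and OS in patients who have high N3RPI". The analysis is introduced with "The following exploratory analyses will be carried out to test this hypothesis", and the method is "Independent Cox PH models will be fit to data from each of the two groups". On content, "The models will include effects for treatment (tarextumab or placebo), NOTCH3 value, and the interaction between treatment and NOTCH3". On output, "The treatment HR and a 95% CI for the HR will be estimated at the quartiles of the NOTCH3 distribution". The same fits are repeated for High and Low groups of Hes1, Hes6, Hey1 and Hey2.

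The shells for Tables 14.2.1.9 (OS) and 14.2.2.7 (PFS) match this. Each has a High and a Low row per marker, a treatment coefficient, a treatment-by-Notch3 coefficient, and three hazard ratios with CIs. The footnote describes "Cox proportional hazards models with effects for treatment, Notch3 and treatment-by-Notch3 interaction". There is no column or row for a High-versus-Low contrast.

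Sections 8.1 (PFS), 8.3 (ORR) and 8.6 (OS) plan a treatment-by-biomarker interaction for each of Notch3, Hes1, Hey2, Hey1 and Hes6. N3RPI is not in that list. Section 5.4 says "Subgroup analyses by baseline Notch3, Hes1, Hey2, Hey1 and Hes6 expression levels are not planned" and refers to statistical modelling instead.

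**The concern.** The reason given for using N3RPI is that patients with high and low scores behave differently. Whether the index modifies the effect of tarextumab is a question about the difference between the two treatment effects. The planned output answers two other questions: whether the hazard ratio differs from 1 within each half, and whether it varies with NOTCH3 within each half.

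A drug that works equally in everyone can have a CI that excludes 1 in one half and not in the other, simply because each half holds few events. A reader of the table has no planned figure to guard against taking that pattern as evidence for the index. What is at stake is the reading of an exploratory result. The primary PFS conclusion is not affected.

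Separately, Section 5.4 says subgroup analyses by these markers are not planned, while Section 9 plans High and Low fits for four of them.

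**Working it through.** **The plan's own figure first.** Table 1 gives power 0.8090 for 91 events, HR 0.67 and one-sided alpha 0.15. The Schoenfeld approximation with 1:1 allocation is Φ(√(d/4)·|ln HR| − z). Here √(91/4) × 0.4005 = 1.910, and Φ(1.910 − 1.036) = 0.809. This reproduces the table, so the same approximation is used below. The SAP states no power or error rate for the N3RPI analysis.

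**Inputs.**
- The notes to Table 6 give 89 patients and 58 PFS events, with 56 observations deleted for missing values.
- A median split gives about 58/2 = 29 events per half.
- The SAP does not give the biomarker-evaluable event count at the final analysis. The upper end is taken as 91/2 = 45.5 per half, which assumes that all 91 events have biomarker data.
- The CIs are two-sided 95% (Section 9).

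**Approximation, uniform HR 0.67.**
- 29 events per half: √(29/4) × 0.4005 = 1.078. P(CI below 1) = 1 − Φ(1.96 − 1.078) = 0.189. Exactly one half: 2 × 0.189 × 0.811 = 0.307. High only: 0.153.
- 45.5 events per half: P(CI below 1) = 0.271. Exactly one half: 0.395. High only: 0.198.

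**Simulation of the SAP's models.** Treatment, NOTCH3 and their interaction were fitted separately in each half. Markers were assumed independent, normal and not prognostic, and no marker modified the treatment effect. There were 4,000 runs at 89 patients and 58 events, and 3,000 runs at 145 patients (89 + 56) and 91 events. The last column is a pooled treatment-by-group test at two-sided 0.05.

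| Uniform HR | Setting | Exactly one half below 1: median / any quartile | High only: median / any quartile | Treatment-by-group test |
|---|---|---|---|---|
| 1 | 58 events | 5.5% / 10.7% | 2.9% / 5.6% | 4.9% |
| 0.75 | 58 events | 21.5% / 30.3% | 10.4% / 14.9% | 5.9% |
| 0.67 | 58 events | 28.1% / 36.8% | 13.5% / 18.2% | 4.8% |
| 0.50 | 58 events | 47.2% / 49.9% | 23.6% / 24.7% | 5.1% |
| 0.67 | 91 events | 37.4% / 45.1% | 19.2% / 22.8% | 4.9% |

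**Precision of the missing contrast.** The halves share no patients, so the SE of the difference in log hazard ratios is about √(4/29 + 4/29) = √(8/29) = 0.525. With 45.5 events per half it is 0.419.
- The 95% CI for the ratio of hazard ratios spans a factor of exp(1.96 × 0.525) = 2.80 either way, or 2.27 with 45.5 per half.
- Under a uniform effect the two estimates differ by a factor of 1.5 or more with probability 2 × [1 − Φ(0.405/0.525)] = 44%, or 33% with 45.5 per half.
- Power to detect a true ratio of 0.5 is Φ(0.693/0.525 − 1.96) = 26%, or 38% with 45.5 per half.

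**The case against.** The plan has several good answers.

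1. **The hypothesis as worded is benefit within High N3RPI.** The High model estimates that directly, and its treatment-by-NOTCH3 term addresses the proposed mechanism. This stands. It does not cover the step from benefit in High to an effect that depends on the index, which needs the comparison with Low.

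2. **The single markers are already covered.** A reader might infer that every High/Low split lacks an interaction analysis. The documents do not support that. Sections 8.1, 8.3 and 8.6 model the interaction on the continuous scale, which keeps more information than a median split.

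3. **Chance alone is not a large problem for N3RPI.** A reader might infer that with an inactive drug the index would often look predictive. At HR 1 the hypothesised High-only pattern appears in 2.9% of trials at the NOTCH3 median and 5.6% at any quartile. Much larger rates arise only by pooling all 30 CIs in a table (five splits, two levels, three quartiles) and counting those that favour placebo.

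4. **The 28% to 37% includes trials where only Low shows benefit.** This is fair. The pattern that matches the hypothesis occurs in 13.5% to 18%, still well above 5%.

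5. **The ratio can be derived from the two reported fits.** This is true if both use the same NOTCH3 values, and a test built that way rejected in 6% to 7% of simulated trials with a uniform effect. However, Section 9 does not say whether the quartiles are overall or within each half, and a contrast left to the reader is not prespecified.

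6. **The analysis is labelled exploratory, and the shells show CIs without p-values or a decision rule.** This stands. The risk is a misreading, not a false confirmatory claim.

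**Conclusion.** The point holds for N3RPI. No planned analysis estimates whether the treatment effect differs between High and Low N3RPI, although such a difference is the motivation for the index. At the design hazard ratio of 0.67, applied uniformly, exactly one half would show a CI below 1 in about 28% of trials at the NOTCH3 median and 37% at any quartile. The High-only figures are 13.5% and 18%. A treatment-by-group test rejects in about 5%.

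These figures rest on about 29 events per half, on independent normal markers, and on reading a CI below 1 as evidence of benefit. That reading is an assumption, not a rule in the SAP. With 45.5 events per half the exactly-one-half figures rise to 37% and 45%.

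The conflict between Sections 5.4 and 9 over Hes1, Hes6, Hey1 and Hey2 is plain from the text. Overall this is an inexpensive improvement to an exploratory analysis, not a flaw in the primary inference.

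**What to change.** - Keep the within-half hazard ratios in Section 9 as descriptive results.
- For N3RPI, add one Cox model in all biomarker-evaluable patients, stratified by or including N3RPI group. It should contain treatment, NOTCH3, their interaction, NOTCH3-by-group, treatment-by-group and treatment-by-NOTCH3-by-group. Centre NOTCH3 at its overall median, so that the treatment-by-group term gives the ratio of the High to Low treatment hazard ratios at that value.
- Report that ratio with its 95% CI as an added column or row in Tables 14.2.1.9, 14.2.1.10, 14.2.2.7 and 14.2.2.8. State that the NOTCH3 quartiles are those of the whole biomarker set.
- Say that any statement about N3RPI modifying the treatment effect will rest on this estimate and its CI, not on which half's CI excludes 1. Note the low precision (26% to 38% power for a ratio of 0.5). For that reason a significance requirement on the contrast is not proposed.
- Amend Section 5.4 to acknowledge the exploratory High/Low fits for Hes1, Hes6, Hey1 and Hey2, or remove those fits from Section 9.

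The cost is a paragraph in the SAP and one added column or row in four tables, with no new data. The downside is that the contrast will be imprecise, so fewer positive biomarker statements can be made.
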